4.4 Preparation and Administration of Study Drug

Study medication Vitamin D₂ and comparator, will be ordered and manufactured directly by a 503b compounding pharmacy (i.e., Pharmacy Innovations) and shipped to each site's investigational drug pharmacy (IDS). All medication will be stored in a climate-controlled storage area. The containers will be labeled by the manufacturer and each IDS will receive 2 bottles (active and placebo). The IDS will store and administer each dose, depending on the arm the participant is randomized into. Each participant will receive 2 capsules of indistinguishable active study drug or placebo.

4.5 Subject Compliance Monitoring

Administration of the study drug will be completed by ED nursing staff and will be documented in the medication administration record (MAR). Reasons for refusal will be documented in the MAR. If the participant does not receive study drug but is randomized, they will be excluded from subsequent analysis.

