3.6 Inclusion Criteria

1. ≥ 18 years and ≤ 65 years of age
2. Admitted to ED within 24 hours of motor vehicle collision
3. Plan to discharge to home from the emergency department
4. Stated willingness to comply with all study procedures and availability for the duration of the study (with the exception of the blood draw sample collected in the ED, which is optional)
5. Has a smartphone with continuous service ≥ 1 year
6. Able to speak and read English
7. Alert and oriented, and capable of engaging in informed consent
8. Willing to take on-time dose of study medication (2 capsules of Vitamin D or placebo)
9. Non-Hispanic white or non-Hispanic black
10. Point of care Vitamin D level <100 ng/ml
11. During ED admission pain severity must be at least 4/10 or higher

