3.9.2 Data Collection and Follow-up for Withdrawn Subjects

If the patient voluntarily withdraws from the study, outcome measures from completed timepoints will be collected and included in intention to treat analysis. If the patient is lost to follow-up and is unresponsive to more than 3 phone calls and 3 secure e-mails, the next of kin listed in the medical record will be contacted once to attempt to reach the participant. If this is not successful, then 1 final email will be sent to attempt to contact the consented participant.

Study Drug

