4.2 Treatment Regimen

Within 24 hours of presenting to the ED for a MVC, and immediately following enrollment in this study, participants will be provided with study drug or placebo. The study drug and placebo will be manufactured and encapsulated by a 503b compounding pharmacy (i.e., Pharmacy Innovations), and will ship the study drug to the investigational pharmacy at each study site. Immediately following randomization, the IDS pharmacy will receive an email with the unblinded treatment allocation for the participant. The IDS at each site will dispense the appropriate study drug once they receive a prescription from the clinician at enrollment. Study medications (placebo or active) will be administered orally via a one-time dose that will be observed by the research personnel in the ER.

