4.3 Method for Assigning Subjects to Treatment Groups

Once a potential subject has been successfully screened, does not meet any exclusion criteria, is willing to participate in the study, and signs informed consent, the participant will be randomized by the study site using a minimization algorithm stratified on race, sex, and pain score. Randomization of participants using minimization will be accomplished using a centralized, web-based, validated (compliant with FDA 21 CFR Part 11) service (randomize.net). In this algorithm, a new participant is sequentially assigned to a particular treatment group by taking into account the covariates of the current and previously randomized participants. To further optimize power in this small, pilot study to examine the effect of race, and achieve a main goal of this study, a 1:1 ratio of non-Hispanic Black and White Americans will be enrolled. Once enrollment reaches 45 in a given race strata (e.g., non-Hispanic Black), enrollment for that race will cease. All participants, investigators, study

personnel, and follow-up team members will be blinded to allocation and concealment will be maintained throughout the study. Only the investigational pharmacy and study statistician will be unblinded to the drug the participant is receiving. They will not reveal this to the patient care team, investigative team, or to the participant. Dosing schedule, route of administration, number of pills in each dose, and the appearance of the capsules will be identical among each group.

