Analysis plan Overall efficacy (a) will be addressed by evaluating for evidence that Vitamin D administration per protocol vs. placebo decreases overall MSP scores across study timepoints. The effect of the intervention on overall pain over time will be assessed by evaluating the coefficient for treatment group (β_1) in the model: $P_{ij} = \beta_0 + \alpha_{0i} + \beta_1 \text{Treatment}_i + \beta_2 \text{Race}_i + \beta_3 (\text{Treatment} \times \text{Race}) + \varepsilon_{ij}$, where P_{ij} is the pain score for the i th individual at time point j , β 's denotes fixed effects, α_{0i} is the random intercept for the i th individual and ε corresponds to random errors. Narrowing of racial disparity will be addressed by evaluating the interaction between race and treatment (β_3 in model above). Specifically, as described above we will assess whether Vitamin D has greater effect on pain outcomes over time in Blacks than Whites. All analyses will be evaluated on the basis of intention to treat. Prior to

[figure not shown]

Figure 2. Plot demonstrating power to detect a main effect (β_1 , black lines) and interaction (β_3 , blue lines) across a range of sample sizes, at three effect sizes estimated using simulation data generated from previous studies. Vertical red line indicates sample size proposed here (n=90). This demonstrates the power to assess Aim 2a (black) and 2b (blue).

data un-blinding, the study statistician will perform a blind review of the data in which statistical models will be developed and tested using dummy (computer-generated) treatment assignments. This is to ensure important covariates are added to the model prior to un-blinding to eliminate any bias of model covariate selection on results. After un-blinding the data, we will use appropriately specified linear contrasts of model parameters to estimate mean differences between participants treated with Vitamin D and placebo and 95% confidence intervals.

Power Estimates of power were derived using a Monte Carlo simulation based on parameter estimates from our observational data of MVC survivors using R (v. 4.0.2⁴⁸); and the *simr* package (v. 1.0.5⁴⁹). The power across a range of effect sizes for the main effect (a) is shown in Figure 2. These data and analysis must be seen as general estimates given that we lack intervention data for this population/condition.

Secondary Analyses:

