6.2 Subject Population(s) for Analysis

We will examine effect of Vitamin D on pain outcomes using an intention to treat paradigm. Participants will be analyzed in the group in which they are randomized.

Safety and Adverse Events

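### Section 4.5 drops randomised but undosed patients from analysis, while sections 6.1 and 6.2 promise intention to treat; no analysis set reconciles them

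*Combined protocol and SAP*

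**What the plan says.** The exclusion is in section 4.5 (Subject Compliance Monitoring): "If the participant does not receive study drug but is randomized, they will be excluded from subsequent analysis". It is not limited to any endpoint or analysis. The sentence before it foresees the case: "Reasons for refusal will be documented in the MAR".

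The analysis sections say something else. Section 6.1, in the efficacy analysis paragraph: "All analyses will be evaluated on the basis of intention to treat". Section 6.2 (Subject Population(s) for Analysis): "We will examine effect of Vitamin D on pain outcomes using an intention to treat paradigm". Section 6.2 adds that patients are analysed in their randomised arm. Neither section sets a dosing condition or refers to 4.5.

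Section 3.9.2 says of patients who withdraw that "outcome measures from completed timepoints will be collected and included in intention to treat analysis".

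For feasibility, sections 3.4 and 6.1 require more than 80% of participants to be retained to 3 months, without saying whether that means randomised or dosed participants. Section 6.1 expects follow-up of about 80% and computes its precision with n=90.

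**The concern.** Intention to treat, stated without qualification, is normally read as including every randomised patient. Section 4.5 removes some of them for a reason that arises after randomisation. The result is a randomised-and-dosed set that has no name and that the analysis sections do not mention. The primary pain population then depends on which section the analyst follows.

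The case can occur. Dosing comes after randomisation (section 5.1), section 4.5 provides for refusals, and section 4.2 says "The IDS at each site will dispense the appropriate study drug once they receive a prescription from the clinician at enrollment". No replacement rule is given, and section 4.3 closes recruitment by race: "Once enrollment reaches 45 in a given race strata". An excluded patient is therefore not made up.

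Two things are at stake: which patients enter the primary pain model, and whether a primary feasibility criterion is met when the expected value lies on the threshold.

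**Working it through.** **Text comparison**

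| Section | Randomised but undosed patient | Scope |
|---|---|---|
| 4.5 | Excluded | Any later analysis |
| 6.1 | Included on the usual reading of ITT | All analyses (stated in the efficacy paragraph) |
| 6.2 | Included on the usual reading of ITT | Pain outcomes |
| 3.9.2 | Completed timepoints kept if the patient withdraws | ITT analysis |

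The conflict with 3.9.2 is indirect: it needs a patient who is undosed and also withdraws. That patient's ED pain score is collected before randomisation (5.1) and is one of the modelled timepoints (6.1). Section 3.9.2 keeps it and 4.5 removes it.

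**Inputs.** From the documents: N = 90, allocated 1:1 and so about 45 per arm; expected follow-up about 80%; retention criterion >80%. Not in the documents: the number undosed, k. I assume k = 1 to 3.

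**The plan's own figure.** Half-width of the 95% CI for follow-up: 1.96 × √(0.8 × 0.2 / 90) = 8.26 points. This matches the stated ±8.3%, so that figure counts all 90.

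**Pain precision.** The standard error ratio is about √(90/(90 − k)): 1.006 for k = 1, 1.011 for k = 2 and 1.017 for k = 3.

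**Pain effect.** Suppose all k undosed patients are in the active arm, complete the surveys and get no effect. The ITT effect is then (1 − k/45) of the dosed-only effect: 44/45 = 97.8% for k = 1 and 42/45 = 93.3% for k = 3. This is an extreme case.

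**Retention pass marks.** The smallest count above 80% is 73 of 90, 72 of 89, 71 of 88 and 70 of 87. With 72 completers, 72/90 = 80.0% does not exceed 80%, while 72/89 = 80.9% does.

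**Chance that the exclusion changes the retention result.** Let X be the number of completers among the other 90 − k patients, X ~ Binomial(90 − k, p). If all k undosed patients fail to complete, the two denominators disagree when X reaches the smaller pass mark but not 73:

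- k = 1, X = 72: 10.5% at p = 0.80 (4.5% at 0.75, 6.2% at 0.85)
- k = 2, X = 71 or 72: 20.6% at p = 0.80
- k = 3, X = 70 to 72: 30.0% at p = 0.80

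If all k undosed patients complete, the all-randomised rule needs X + k ≥ 73, that is X ≥ 72, 71 or 70 for k = 1, 2 or 3. These equal the dosed-only pass marks, so the result never changes.

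Between these ends, with p = 0.80 and k = 1, 2, 3:

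| Completion among the undosed | k = 1 | k = 2 | k = 3 |
|---|---|---|---|
| 0% | 10.5% | 20.6% | 30.0% |
| 50% | 5.2% | 10.4% | 15.6% |
| 80% | 2.1% | 4.2% | 6.3% |
| 100% | 0% | 0% | 0% |

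**The case against.** The strongest reply is that 4.5 is the only place with an explicit rule for undosed patients, and that the 6.2 statement about the randomised group governs the arm, not who is included. Read together, the sections would describe a modified ITT set that lacks a name, and the defect would be one of labelling. Such a set can be defended. But the plan neither names nor defines it, and 6.1 and 6.2 state ITT without qualification, so the reader has to infer it.

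Several points about size stand:

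- Undosed patients should be few. An inclusion criterion in section 3.6 is "Willing to take on-time dose of study medication", and the single dose is observed (4.2, 5.2).
- Blinding and identical capsules (4.3) make exclusion largely independent of arm. This is not fully assured, because the dispensing pharmacy receives the unblinded allocation before dosing (4.2).
- The 10.5% to 30.0% figures are worst cases: they require undosed patients to exist and all of them to miss follow-up. Section 4.5 does not say that their surveys stop.
- Retention of 80.0% against 80.9% is a small difference beside ±8.3 points, and no go/no-go decision is tied to the threshold.
- No ITT statement clearly governs retention. Sections 3.2 and 3.4 describe the 90 as patients given study drug, but as planned flow and a target. For retention the fault is therefore an undefined denominator, which the unlimited wording of 4.5 makes worse, and not a direct contradiction.

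None of this removes the conflict between 4.5 and 6.1/6.2.

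**Conclusion.** The concern holds. The exclusion in 4.5 contradicts the intention-to-treat rule in 6.1 and 6.2, and no named set reconciles them. This rests on the text alone and is held with high confidence.

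The sizes are less certain because they depend on an assumed 1 to 3 undosed patients. On that assumption the effect on the pain estimate is modest. For retention at 80% follow-up, the chance that the choice of denominator decides the result runs from zero, if all undosed patients complete, to 10.5%, 20.6% or 30.0% for one, two or three undosed non-completers. The plan should be corrected before unblinding, since a set chosen afterwards would be open to bias.

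**What to change.** Replace the exclusion sentence in 4.5. State that all randomised participants stay in the primary ITT pain analysis and in the retention denominator, and that undosed participants are followed through the existing surveys. Report the number randomised but not dosed, by arm. Label any randomised-and-dosed (modified ITT) pain analysis as supportive.

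If the team prefers a randomised-and-dosed primary set, name and define it in 6.1 and 6.2 in place of the unqualified ITT wording, and add an all-randomised sensitivity analysis.

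For the criterion on vitamin D levels in the treatment group, state which denominator applies. A dosed set is acceptable there if it is named.

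The cost is one replaced sentence in 4.5 and one statement of analysis sets and denominators in 6.1/6.2. The REDCap surveys simply continue for any undosed participants; no new instruments or visits are needed.

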4.6 Prior and Concomitant Therapy

Prior and concomitant analgesic and anti-inflammatory treatments will be collected on enrollment, discharge from the hospital through data extraction, and at each REDCap survey follow-up assessment. Analgesic medications as would be normally prescribed are permitted throughout this study including anti-inflammatory agents. Consumption of medication will be tracked and addressed in secondary analyses.

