3.7 Exclusion Criteria

1. Substantial comorbid injury (e.g., long bone fracture)
2. Pregnancy/breastfeeding
3. Prisoner status
4. Chronic daily opioid use prior to MVC (>20 mg oral daily morphine equivalents)
5. Active psychosis, suicidal ideation, or homicidal ideation
6. Plans for hospital admission
7. Known chronic kidney disease, stage 4 or higher ($GFR \leq 29$)
8. Intubated and sedated at time of enrollment
9. Inability to provide informed consent (receipt of sedative, hypnotic agent making the patient non-decisional for consent)
10. Known hypercalcemia
11. Vitamin D supplements in excess of 800 IU daily

12. Any other history or condition that would, in the site investigator's judgement, indicate that the patient would very likely be non-compliant with the study or unsuitable for the study (e.g., might interfere with the study, confound interpretation, or endanger patient)

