5.1 Enrollment Procedures

This first visit will take place upon admission to the hospital following MVC within 24 hours of the collision. Patients who meet inclusion criteria/exclusion criteria based on a review of the electronic medical record by research assistants, participants will be approached for participation. If the patient is interested in participating, they will then undergo informed consent. At this point in time, the participants will undergo baseline assessments (administered through REDCap) and collections of point of care Vitamin D levels with blood spot card. The participants will also have the option to consent to collect additional blood during a standard of care procedure while in the ED. The study would collect an EDTA tube,

a sodium heparin tube, and PAX gene RNA and DNA tubes. Patients with a Vitamin D level <100 ng/ml, will then take the baseline questionnaire. After all baseline data is collected, participants will be randomized and then administered appropriate study medication (Vitamin D or placebo). This administration will be documented in the MAR. Patients will be given a paper copy of their consent. Upon discharge of the patient, the patient will be given supplies to perform a home fingerstick blood draw (similar to one collected in the ED for baseline) and blotting on a blood spot card, which will occur at the 3-month timepoint.

Medical record information abstracted at time of admission will include information related to patient past medical history and initial motor vehicle collision care, and medication use prior to admission and prior to enrollment. Laboratory values relevant to patient renal and hepatic function will also be recorded (if obtained) along with any toxicology labs obtained by the primary treating team.

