Demographic and phenotypic data will be collected at this time. Patients will be asked to report demographic information including age, sex, ethnicity, education level, income level, and marital status. In addition, patients will be administered an enrollment survey which will collect domains important to the pain experience. These are listed in table 2. All patient information will be recorded by a trained research assistant or the patient via direct entry. We will assess treatment expectation using a modified survey that uses Likert scales prior randomization. In addition, we will administer weekly surveys of pain severity and to assess whether adverse events are experienced weekly through 6 weeks (these brief surveys will be sent at 2 weeks, 4 weeks and 5 weeks). Adverse events will also be monitored at 3 weeks, 6 weeks, and 3 months following administration of study drug.

Table 2. Assessments by domain at each timepoint

Domain	Measure	D1	3W	6W	3M
Demographic information	Age, sex, gender, race/ethnicity, education, income, marital status	●			
Pre-MVC	Pain catastrophizing scale ²⁶ , PROMIS Item Bank v1.0 - Emotional Distress – Anxiety ²⁷ , PROMIS Item Bank v1.0 - Emotional Distress - Depression ²⁷ , Anxiety Sensitivity Index ⁵¹	●	●	●	●
Traumatic Event	Details of Traumatic Event, Concussion, Traumatic Brain Injury, Life events checklist ²⁸	●			
MVC Injury Severity	Abbreviated injury scale ²⁹	●			
Pain	Numeric Rating Scale, [†] RPS ³⁰ , PROMIS Short Form v1.0 - Pain Interference 4a ³¹ , PROMIS Scale v2.0 - Neuropathic Pain Quality 5a ³² , PROMIS Scale v2.0-Nociceptive Pain Quality 5a	●	●	●	●
Somatic Symptoms	Pennebaker Inventory of Limbic Languidness ⁵²	●	●	●	●
Global Mental and Physical Health	PROMIS Scale v1.2 - Global Mental 2a ³³ , PROMIS Scale v1.2 - Global Physical 2a ^{33,34}	●	●	●	●

Anxiety/Depressive Symptoms	PROMIS Item Bank v1.0 - Emotional Distress – Anxiety ²⁷ , PROMIS Item Bank v1.0 - Emotional Distress - Depression ²⁷	●	●	●	●
Posttraumatic stress symptoms	PTSD Symptom Severity index-interview for DSM-5 ³⁵ , Peritraumatic Distress Inventory items (PDI) ⁵³	●	●	●	●
Dissociative Symptoms	Michigan Critical Events Perception Scale ³⁶	●			
Analgesic Medication Use	Daily milligram morphine equivalents, non-opioid analgesic use, Date of opioid cessation (first day in three consecutive where patient took no opioids) ³⁷ .	●	●	●	●
Substance abuse	PROMIS Short Form v1.0 - Severity of Substance Use (Past 30 days) 7a ³⁸	●	●	●	●

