5.3 Data Extraction

Medical record information abstracted after discharge will include information on the patient's health status and care during hospitalization and at the time of discharge. This information will include MVC characteristics, medications taken during emergency department admission, and discharge medications. All data extraction will be stored in REDCap.

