6.1 Outcome definitions/Analysis plan/Power calculation

Assess the feasibility of the RCT protocol by (a) calculating recruitment rate and participant retention, and (b) measuring the ability of Vitamin D administration to generate sustained increases in whole-blood Vitamin D concentrations (assessed 3 months after MVC).

Outcome definitions for Feasibility will be determined by the ability of the study team to: recruit 90 patients into the trial over the 15-month recruitment period, retain >80% of participants through 3-month follow-up, and achieve Vitamin D levels >20 ng/ml in 90% of treatment group at 3-month follow-up. In addition, will determine whether Vitamin D

administration per protocol can raise Vitamin D concentration in treatment group > 10ng/ml above baseline.

Analyses: Feasibility analyses will be performed using descriptive statistics. To assess Vitamin D increase according to treatment group, paired t-test will be used.

Power: Based on our previous Vitamin D trial and other work,⁴⁰⁻⁴⁵ we estimate that observed follow-up will be ~80%. With n=90 sample, this will permit follow-up rates estimates at 3 months with 95% CI $\pm 8.3\%$. This will permit assessment of follow-up feasibility and necessary sample size for an R01 RCT, if pilot results warrant. In addition, based on our previous Vitamin D trial, assuming 80% retention and Vitamin D concentration standard deviation of 4ng/ml, we will have >99% power to detect a change of 10 ng/ml in Vitamin D level in the treatment group.

Assess **preliminary efficacy** of Vitamin D administration per protocol to (a) decrease overall MSP severity during the 3 months following MVC, and (b) reduce MSP outcome disparity between Blacks vs. Whites following MVC.

Outcome Definitions for Pain Reduction between treatment groups will be assessed using patient-reported overall MSP scores (0-10 NRS) obtained at the ED, 3-week, 6-week, and 3-month assessments. NRS scores are valid measures of pain assessment.^{46,47}

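### Vitamin D supplement use between discharge and 3 months is not specified for collection, so the within-arm Vitamin D feasibility criteria cannot separate the study dose from new off-study intake

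*Combined protocol and SAP*

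**What the plan says.** On collection, section 4.6 states that "Prior and concomitant analgesic and anti-inflammatory treatments will be collected on enrollment", at discharge and at each follow-up survey. The section closes with "Consumption of medication will be tracked and addressed in secondary analyses". Table 2 in section 5.1 turns this into one follow-up row, "Daily milligram morphine equivalents, non-opioid analgesic use, Date of opioid cessation", at day 1, 3 weeks, 6 weeks and 3 months. It has no supplement row. The brief surveys at 2, 4 and 5 weeks (section 5.4) cover pain and adverse events.

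Chart abstraction covers "medication use prior to admission and prior to enrollment" (section 5.1) and "medications taken during emergency department admission, and discharge medications" (section 5.3). Neither reaches past discharge.

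Supplements are named once, in the exclusion criteria (section 3.7): "Vitamin D supplements in excess of 800 IU daily". Use up to that amount is allowed at entry. Nothing is said about use afterwards.

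On analysis, sections 3.4 and 6.1 set two Vitamin D feasibility criteria, both for the treated arm: 90% of participants above 20 ng/ml at 3 months, and a rise of more than 10 ng/ml from baseline. Section 6.1 adds: "To assess Vitamin D increase according to treatment group, paired t-test will be used". Sections 3.2 and 3.4 also provide for levels to be measured before and after treatment in both arms.

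**The concern.** The 3-month level is a primary feasibility endpoint, and over-the-counter Vitamin D acts on it directly. Participants consent to a Vitamin D trial and have a Vitamin D test in the ED, so some may start a supplement. The documents do not say whether the test result is disclosed, and they give no rate of such use.

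A criterion based on the treated arm alone, or a before-after test, counts any new intake as an effect of the dose. That could carry a pilot over its success threshold and misinform the larger trial it is meant to support (section 2.3). In the other direction, if the contrast between arms came out weak, the team could not tell an insufficient dose response from supplement use in the placebo arm. The exploratory analysis in section 2.2 relating Vitamin D level to pain trajectory is not a randomised comparison, so self-selected supplement use could confound it as well. Exposure that is never recorded cannot be recovered at the analysis stage.

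**Working it through.** **Inputs from the documents.** 90 participants randomised 1:1, so 45 per arm (section 3.2); 80% retention and SD 4 ng/ml (section 6.1); expected rise about 9 ng/ml (sections 1.2 and 1.4); threshold 10 ng/ml (sections 3.4 and 6.1).

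**Assumptions.** Two-sided alpha of 0.05, as none is stated. A share *f* of an arm starts a supplement, with mean rise *r* ng/ml in those who start. The 10 ng/ml criterion is read as applying to the arm mean, which the documents do not state.

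**Step 1: the plan's own figures.** n = 45 × 0.80 = 36. Noncentrality = 10 / (4/√36) = 15, so power = Φ(15 − 1.96), above 99% as stated. If 4 is the SD of a single level and the two levels are uncorrelated, the SD of change is 4√2 = 5.66, noncentrality is 10.6, and power is still above 99%. The follow-up half-width is 1.96 × √(0.8 × 0.2/90) = 8.26%, matching the stated 8.3%.

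**Step 2: the treated-arm threshold.** The mean shift from off-study use is f × r. With f = 10% and r = 10, or f = 20% and r = 5, the shift is 1 ng/ml and the expected rise becomes 9 + 1 = 10. Any larger shift takes it past the threshold.

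**Step 3: the paired test when the dose does nothing.** The SD of change becomes √(16 + f(1−f)r²). Noncentrality = f·r / (SD/√36), with 35 degrees of freedom. The changes would then be a mixture rather than normal, so the rates are approximate.

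| f | r (ng/ml) | Shift | SD | Chance of a significant result |
|---|---|---|---|---|
| 10% | 5 | 0.5 | 4.27 | 10.5% |
| 10% | 10 | 1.0 | 5.00 | 21.5% |
| 20% | 5 | 1.0 | 4.47 | 25.7% |
| 20% | 10 | 2.0 | 5.66 | 54.1% |
| 30% | 10 | 3.0 | 6.08 | 82.0% |
| 50% | 10 | 5.0 | 6.40 | 99.5% |

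The nominal rate is 5%.

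**Step 4: the randomised contrast, 36 against 36.** SE = SD × √(2/36), and power = Φ(difference/SE − 1.96).

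- *Equal use in both arms.* The shifts cancel and the expected difference stays 9 ng/ml. For f from 10% to 50% and r from 5 to 15, power stays above 99%. The lowest value is at f = 50%, r = 15: SD 8.50, SE 2.00, power 99.4%.
- *Use in the placebo arm only (an extreme case).* The difference is 9 − f·r. At f = 20%, r = 10 it is 7.0 and power is above 99%. At f = 30%, r = 15 it is 4.5 and power is 67%. At f = 50%, r = 15 it is 1.5 and power is 11%. The inflated SD is applied to both arms here, which is conservative.

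The within-arm results are therefore sensitive to modest use. The randomised contrast is hidden only by heavy and strongly unequal use.

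**The case against.** The strongest reply is that randomisation already deals with this. The trial is double-blind and placebo-controlled, with 3-month levels in both arms. Use that is balanced across arms cancels in the difference, and widespread use among placebo participants would show as a rise in that arm. This stands. A reader might infer from the missing item that neither a rise nor a lack of contrast could be attributed to the dose, or that off-study use could not be detected at all. The documents do not support either reading: the between-arm difference remains attributable to allocation, and the group-level signal is measured. What is missing is the individual record that would explain it, and the stated criteria and test do not use the placebo arm as a comparator.

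Second, the closing sentence of section 4.6 on tracking medication could be read to include supplements. It follows a sentence on analgesics, and Table 2 carries only analgesic use forward, so it does not clearly do so. Because Table 2 lists domains rather than survey items, the fair statement is that collection is not specified.

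Third, stable use within the entry limit is largely contained in the baseline level and mostly drops out of a change. This also stands: only new or increased use matters, and its frequency is unknown.

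Fourth, it is tempting to size the problem by adding up daily intake over three months and comparing the total with the single doses in Table 1. That equates daily with single-dose intake, which no section supports. Table 1 itself shows no simple relation between total dose and rise: 100,000 IU is listed with a 13 ng/ml rise at 6 weeks, and 600,000 IU with 6 ng/ml at 4 weeks. No such conversion is used here.

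**Conclusion.** The point holds in limited form. Supplement use between discharge and the 3-month blood spot is not specified for collection, and the Vitamin D criteria and paired test, being treated-arm or within-arm, cannot separate the dose from new off-study intake. The margin is thin: about 9 ng/ml expected against a threshold of 10, so an assumed mean shift of 1 ng/ml reaches it. With no dose effect and 20% of the arm rising by 10 ng/ml, the paired test would be significant about 54% of the time.

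These sizes rest on assumed values of *f* and *r* and show sensitivity only; they do not predict how many participants would take supplements. The validity of the randomised comparison and the stated power are not in question. The remaining loss on that side is interpretive: an unexpectedly weak contrast could not be explained. The change is worth making because the data cannot be recovered later and the cost is small.

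**What to change.** 1. Add one item on Vitamin D or multivitamin use (product, daily IU, start date) to the enrolment, 3-week, 6-week and 3-month surveys. If the tracking sentence in section 4.6 was meant to cover supplements, say so there and in Table 2.
2. Tabulate reported use by arm and time point.
3. In section 6.1, report the baseline-adjusted between-arm difference in 3-month level, with its 95% confidence interval, alongside the within-arm criteria. This uses data already planned.
4. Use supplement data only in a sensitivity analysis labelled as such. Supplement use is a post-randomisation variable, so excluding participants who start one breaks the randomised comparison and departs from the intention-to-treat principle in sections 6.1 and 6.2.

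The cost is one extra survey item in surveys already scheduled and a small amount of analysis. Sample size and stated power do not change.
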